16.4.2. Treatment Emergent Flag for Adverse Events

Flag	Definition
Treatment Emergent	
 • Study Treatment Start Date \leq AE Start Date • AE Start Date is missing

NOTES:

- If the study treatment stop date is missing, then the AE will be considered to be On-Treatment.
- Time of study treatment dosing and start/stop time of AEs should be considered, if collected.

16.5. Appendix 5: Data Display Standards & Handling Conventions

16.5.1. Reporting Process

Software	

 The currently supported versions of SAS software will be used. 	
Reporting Area	
HARP Server	: US1SALX00259
HARP Compound	: arprod\gsk2859716\bma117159\
Analysis Datasets	

 Analysis datasets will be created according to CDISC standards (SDTM IG Version 3.1.3 & ADaM IG Version 1.0). 	
Generation of RTF Files	

 RTF files will be generated for all tables. 	

16.5.2. Reporting Standards

General	

 The current GSK Integrated Data Standards Library (IDSL) will be applied for reporting, unless otherwise stated (IDSL Standards Location: https://spope.gsk.com/sites/IDSLLibrary/SitePages/Home.aspx): 
 4.03 to 4.23: General Principles 5.01 to 5.08: Principles Related to Data Listings 6.01 to 6.11: Principles Related to Summary Tables 7.01 to 7.13: Principles Related to Graphics Do not include subject level listings in the main body of the GSK Clinical Study Report. All subject level listings should be located in the modular appendices as ICH or non-ICH listings 	
Formats	

 GSK IDSL Statistical Principles (5.03 & 6.06.3) for decimal places (DP's) will be adopted for reporting of data based on the raw data collected, unless otherwise stated. Numeric data will be reported at the precision collected on the eCRF. The reported precision from non eCRF sources will follow the IDSL statistical principles but may be adjusted to a clinically interpretable number of DP's. 	
Planned and Actual Time	

 Reporting for tables, figures and formal statistical analyses: 
 Planned time relative to dosing will be used in figures, summaries, statistical analyses and calculation of any derived parameters, unless otherwise stated. The impact of any major deviation from the planned assessment times and/or scheduled visit days on the analyses and interpretation of the results will be assessed as appropriate. Reporting for Data Listings: 
 Planned and actual time relative to study drug dosing will be shown in listings (Refer to IDSL Statistical Principle 5.05.1). Unscheduled or unplanned readings will be presented within the subject's listings. 	

Unscheduled Visits	

 Unscheduled visits will not be included in summary tables and/or figures. For by planned time analysis, unscheduled visits will not be included; For worst-case analysis, unscheduled visits will be included. All unscheduled visits will be included in listings. 	
Descriptive Summary Statistics	
Continuous Data	Refer to IDSL Statistical Principle 6.06.1
Categorical Data	N, n, frequency, %
Graphical Displays	

 Refer to IDSL Statistical Principals 7.01 to 7.13. 	

16.5.3. Reporting Standards for Pharmacokinetic Data

Pharmacokinetic Concentration Data	
PC Windows Non-Linear (WNL) File	PC WNL file (CSV format) for the non-compartmental analysis by Clinical Pharmacology Modelling and Simulation function will be created according to SOP_00000314000 : Non-Compartmental Analysis of Clinical Pharmacokinetic Data. Note: Concentration values will be imputed as per GUI_51487
Descriptive Summary Statistics, Graphical Displays and Listings	Refer to IDSL PK Display Standards. Refer to IDSL Statistical Principle 6.06.1. Note: Concentration values will be imputed as per GUI_51487 for descriptive summary statistics/analysis and summarized graphical displays only.
NONMEM/Pop PK File	Pop-PK file (CSV format) for the POP-PK analysis by Clinical Pharmacology Modelling and Simulation function will be created according to the data specification detailed in Section 16.9.1 Population Pharmacokinetic (PopPK) Dataset Specification.
NONMEM/PK/PD File	PK/PD file (CSV format) for the PK/PD analysis by Clinical Pharmacology Modelling and Simulation function will be created according to the data specification detailed in Section 16.10.1 Pharmacokinetic/Pharmacodynamic Dataset Specification.
Pharmacokinetic Parameter Derivation	
PK Parameter to be Derived by Programmer	The following PK parameters will be derived by the Programmer:
Pharmacokinetic Parameter Data	
Is NQ impacted PK Parameters Rule Being Followed	Yes, refer to [Standards for Handling NQ Impacted PK Parameters].
Descriptive Summary Statistics, Graphical Displays and Listings	Refer to IDSL PK Display Standards.

16.5.4. Extended Loss to Follow-up or Extended Time without an Adequate Assessment

For subjects, if two or more scheduled disease assessments are missed and are then followed by an assessment of PD or death, PFS will be censored at the last adequate assessment prior to PD or death. When the scheduled disease assessment is every 3 weeks, a window of 49 days (6 weeks + 7 day window) will be used to determine whether there was an extended time without adequate assessment. That is, if the time difference between PD/death and last adequate assessment is more than 49 days, then PFS will be censored at the last adequate assessment prior to PD/death.

16.5.5. Date Associated with Response

Investigator assessment of disease is entered in the eCRF on the VISIT form. The date of the VISIT is captured but the date of the response assessment is not captured separately. The date associated with response will be the visit date for the VISIT on which the investigator assessed disease. A disease assessment may occur at an unscheduled visit. The date of the unscheduled visit would be assigned to any response assessed on that date. In the following section, unless otherwise specified, the disease assessment denotes post-baseline assessment.

16.6. Appendix 6: Derived and Transformed Data

16.6.1. General

Multiple Measurements at One Analysis Time Point

 • Mean of the measurements will be calculated and used in any derivation of summary statistics but if listed, all data will be presented. • Participants having both High and Low values for Normal Ranges at any post-baseline visit for safety parameters will be counted in both the High and Low categories of Any visit post-baseline row of related summary tables. This will also be applicable to relevant Potential Clinical Importance summary tables.
Study Day

 • Calculated as the number of days from First Dose Date: 
 • Ref Date = Missing → Study Day = Missing • Ref Date < First Dose Date → Study Day = Ref Date - First Dose Date • Ref Date ≥ First Dose Date → Study Day = Ref Date - (First Dose Date) + 1

16.6.2. Study Population

Extent of Exposure

 • Number of days of exposure to study drug will be calculated based on the formula: Duration of Exposure in Days = Treatment Stop Date - (Treatment Start Date) + 1 • Participants who were randomized but did not report a treatment start date will be categorised as having zero days of exposure. • The cumulative dose will be based on the formula: Cumulative Dose = Sum of Dose at Each Cycle • Dose intensity per cycle will be based on the formula: Dose intensity Per Cycle = Cumulative Dose / Total Number of Cycles

16.6.3. Efficacy

Laboratory Parameters
Serum M-protein, Urine M-protein, Serum FLC

 • If a laboratory value which is expected to have a numeric value for summary purposes, has a non-detectable level reported in the database, where the numeric value is missing, but typically a character value starting with '<x' or '>x' (or indicated as less than x or greater than x in the comment field) is present, the number of significant digits in the observed values will be used to determine how much to add or subtract in order to impute the corresponding numeric value. 
 ○ Example 1: 2 Significant Digits = '< x' becomes x - 0.01 ○ Example 2: 1 Significant Digit = '> x' becomes x + 0.1 ○ Example 3: 0 Significant Digits = '< x' becomes x - 1

16.6.4. Safety

Adverse Events
AE'S OF Interest

• Corneal events• Thrombocytopenia• Neutropenia• Hematologic Toxicity• Infusion-related Reactions as collected in the eCRF

16.7. Appendix 7: Reporting Standards for Missing Data

16.7.1. Premature Withdrawals

Element	Reporting Detail
General	
 • Subject study completion (i.e. as specified in the protocol) was defined as: 
 ○ For Part 1 (dose-escalation phase), a completed subject is one who has completed at least 1 cycle of study treatment and an End of Study Visit without events causing them to withdraw or discontinue from the study for reasons listed in Section 6.3 of the protocol. ○ For Part 2 (expansion cohort), a completed subject is one who has received at least one dose of study treatment without events causing them to withdraw or discontinue study treatment for reasons listed in Section 6.3 of the protocol and completed an End of Study Visit. ○ A participant will be considered to have completed the study if he or she has received at least one dose of the study treatment and, has died before the end of the study, has not been lost to follow-up, or has not withdrawn consent from study participation. • Withdrawn subjects may be replaced in the study. • All available data from participants who were withdrawn from the study will be listed and all available planned data will be included in summary tables and figures, unless otherwise specified.

16.7.2. Handling of Missing Data

Element	Reporting Detail
General	
 • Missing data occurs when any requested data is not provided, leading to blank fields on the collection instrument: 
 ○ These data will be indicated by the use of a blank in subject listing displays. Unless all data for a specific visit are missing in which case the data is excluded from the table. ○ Answers such as “Not applicable” and “Not evaluable” are not considered to be missing data and should be displayed as such.
Outliers	
 • Any participants excluded from the summaries and/or statistical analyses will be documented along with the reason for exclusion in the clinical study report.
Responder Analysis	
 • For endpoints which determine the percentage of responders, subjects with unknown/not evaluable or missing best overall response will be assumed to be non-responders, and will be included in the denominator when calculating the percentages.
Time to Event	
 • Because study treatment is dependent on the study endpoints (e.g., progression, i.e. not a fixed treatment duration), the length of treatment for each subject will depend on the efficacy and toxicity of the treatment, so the duration of treatment will vary across subjects. Similarly the duration of follow up will also vary. All available time-to-event data will be analyzed using suitable statistical methods; subjects with shorter treatment and follow-up due to the natural history of their disease or medical necessities of the treatment of their disease will not be considered to have missing time-to-event data.

16.7.2.1. Handling of Missing and Partial Dates

Element	Reporting Detail
General	
 • Partial dates will be displayed as captured in subject listing displays. • Imputed partial dates will not be used to derive study day, duration (e.g. duration of adverse events), or elapsed time variables. In addition, imputed dates are not used for deriving the last contact date in the overall survival analysis dataset. The imputed AE dates will only to be used in the figures “Profile Plot for Patients with No Corneal Event or Grade 1 Corneal Event” and “Profile Plot for Patients with Grade 2 or Higher Corneal Events”. • Imputed dates will not be displayed in listings. However, where necessary, display macros may impute dates as temporary variables for the purpose of sorting data in listings only. In addition, partial dates may be imputed for ‘slotting’ data to study time periods or for specific analysis purposes as outlined below.
Adverse Events	
 • The eCRF allows for the possibility of partial dates (i.e., only month and year) to be recorded for AE start and end dates; that is, the day of the month may be missing. 
 ○ The eCRF allows for the possibility of partial dates (i.e., only month and year) to be recorded for AE start and end dates; that is, the day of the month may be missing. Missing Start Day: First of the month will be used unless this is before the start date of study treatment; in this case the study treatment start date will be used and hence the event is considered On-treatment as per Appendix 4: Study Phases and Treatment Emergent Adverse Events. ○ Missing Stop Day: Last day of the month will be used, unless this is after the stop date of study treatment; in this case the study treatment stop date will be used. • Completely missing start or end dates will remain missing, with no imputation applied. Consequently, time to onset and duration of such events will be missing.
Concomitant Medications	
 • Partial dates for any concomitant medications recorded in the CRF will be imputed using the following convention: 
 ○ If the partial date is a start date, a '01' will be used for the day and 'Jan' will be used for the month ○ If the partial date is a stop date, a '28/29/30/31' will be used for the day (dependent on the month and year) and 'Dec' will be used for the month. • The recorded partial date will be displayed in listings.
Anti-Cancer Therapy (Where applicable), Radiotherapy and Surgical Procedures for Time-to-Event Endpoint and Response	
 • Start dates for follow-up anti-cancer therapy, radiotherapy (where applicable), and surgical procedures (where applicable) will be temporarily imputed in order to define event and censoring rules for progression-free survival, response rate, time to progression, duration of response or time to response (i.e. start date for new anti-cancer therapy). The imputed dates will not be stored on the anti-cancer therapy, radiotherapy, or surgical procedure datasets. • If missing start day, month, and year, then no imputation for completely missing dates • If missing start day and month, then no imputation should be done • If missing start day, then do the following: 
 • If partial date falls in the same month as the last dose of study treatment, then assign to earlier of (date of last dose of study treatment+1, last day of month). • If partial date falls in the same month as the subject’s last assessment and the subject’s last assessment is PD, then assign to earlier of (date of PD+1, last day of month). • If both rules above apply, then assign to latest of the 2 dates • Otherwise, impute missing day to the first of the month. • If missing end date, then no imputation should be done.

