16.4. Appendix 4: Study Phases and Treatment Emergent Adverse Events

16.4.1. Study Phases

Study Phase	Definition
Pre-Treatment	Date ≤ Study Treatment Start Date
On-Treatment	Study Treatment Start Date < Date

Some datasets include the first dosing day as On-Treatment and some exclude the first dosing date as On-Treatment. The first dosing day (Day 1) is considered Pre-Treatment for ECOG, ECG, vital signs, liver events, lab tests, cardiac scan, and other safety domains. The first dosing day (Day 1) is considered to be On-Treatment for adverse events and concomitant medications.

16.4.1.1. Study Time Periods for Concomitant Medications and Blood and Blood Supportive Care Products

Concomitant Medication and Blood and Blood Supportive Care Product start and end dates will be assigned to study time periods in relation to first dose of study treatment as defined below. The start date references time flag variables and end date reference time flag variables will be added to the concomitant medications and blood and blood supportive products datasets, respectively.

- **Start relative to treatment:** Assign to 'BEFORE' if start date is prior to study treatment start date or if subject has not taken any study treatment or (start date is missing and end date is before study treatment start date). Else assign to 'DURING' if the start date falls into the on-therapy period as defined above or if subject is ongoing (not all study treatment discontinuation records completed) or start date is missing. Else assign to 'AFTER' if start date is after the on-therapy period.
- **End relative to treatment:** Assign to 'BEFORE' if end date is prior to study treatment start date or if subject has not taken any study treatment. Else assign to 'DURING' if start date falls into the on-therapy period or if subject is ongoing (not all study treatment discontinuation records completed) or (end date is missing and start relative to treatment not 'AFTER'). Else assign to 'AFTER' if start date is after the on-therapy period or (end date is missing and start relative to treatment='AFTER').

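### Read literally, the date rules flag adverse events as treatment-emergent even when a recorded start month or stop date places them before the first dose

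*SAP*

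**What the plan says.** Four statements in the SAP bear on this.

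- **Section 16.7.2.1, Adverse Events row.** Partial dates can be "recorded for AE start and end dates; that is, the day of the month may be missing", so month and year are known. Where the day of onset is unknown, the rule reads: "First of the month will be used unless this is before the start date of study treatment; in this case the study treatment start" (the sentence goes on to substitute the first-dose date). The row then states the consequence: "in this case the study treatment start date will be used and hence the event is considered On-treatment as per Appendix 4". For dates with no information at all: "Completely missing start or end dates will remain missing, with no imputation applied".
- **Section 16.4.2.** An AE is treatment-emergent if it starts on or after the treatment start date, or if "AE Start Date is missing". Neither criterion refers to the stop date.
- **Section 16.4.1.1** (concomitant medications and blood products). A record is assigned to the period before treatment when, among other conditions, "start date is missing and end date is before study treatment start date".
- **Section 16.7.2.1, General row.** Imputed dates are barred from study day, duration and elapsed time and are not shown in listings. Then: "The imputed AE dates will only to be used in the figures" that profile corneal events (displays 13.0190 and 13.0191 in Section 16.12.9, both Part 2 MM). The row ends by allowing partial dates to be imputed to assign "data to study time periods or for specific analysis purposes as outlined below".

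**The concern.** Moving an incomplete start date to the first dose is a sound conservative convention when the timing relative to treatment is unknown. It is not sound when the recorded information already settles the question. If the recorded month ends before the first dose, every possible start day is pre-treatment. If the event stopped before the first dose, it also started before it. In both situations the rules overwrite what is known instead of filling in what is not.

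Adverse events are part of the primary endpoint (Section 2.2), so the treatment-emergent flag should be right wherever the data allow it. The General row adds a second problem. It confines imputed AE dates to two figures, while the AE row of the same section uses the imputed date to settle On-treatment status.

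**Working it through.** The plan gives no figure to reproduce, so the check is to apply the rules as written to constructed dates.

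**Inputs.** The start-day rule and the missing-date rule come from Section 16.7.2.1, and the flag from Section 16.4.2. The first dose is assumed to be 15 April 2016; the choice of date does not matter to the logic.

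**Rule as written.** If the start day is missing, the imputed start is the later of the first of the recorded month and the first-dose date. The flag is set if the start is missing or is on or after first dose.

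**Rule as corrected.** The first-dose date is substituted only if the recorded month and year are those of first dose and the stop date is missing or on/after first dose. Otherwise the first of the month is used. An event with a missing start is flagged only if its stop date is missing or on/after first dose.

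| Recorded start | Recorded stop | Imputed start as written | Flagged as written | Flagged as corrected |
|---|---|---|---|---|
| March, no day | unknown | 15 April | yes | no |
| January, no day | 10 February | 15 April | yes | no |
| April, no day | unknown | 15 April | yes | yes |
| April, no day | 10 April | 15 April | yes | no |
| missing | 31 March | none | yes | no |
| missing | unknown | none | yes | yes |
| 31 March, complete | unknown | 31 March | no | no |
| May, no day | unknown | 1 May | yes | yes |

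Four of the eight cases change. The cases were chosen to exercise each branch, so 4 of 8 is not an error rate. Three features matter:

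1. An event dated 31 March in full is correctly not flagged, yet the same event recorded only as March is.
2. In the second and fourth rows the imputed start falls after the event's own stop date.
3. The fifth row involves no imputation, so it is misflagged however the General row is read.

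The two ambiguous cases (April with unknown stop; start and stop both missing) stay treatment-emergent under the corrected rule, so the conservative convention is kept where it belongs.

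The SAP already contains both missing guards elsewhere. Section 16.4.1.1 uses the end date for medications and blood products with a missing start. The anti-cancer therapy row of Section 16.7.2.1 moves a partial start date past the last dose only when both fall in the same month.

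**Ceiling on size.** One misflagged event can add at most one subject to a table row:

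- single-subject run-in cohort (Section 3.1.1.1): 1/1 = 100 percentage points
- cohort of three: 1/3 = 33.3 points
- 40 Part 2 MM subjects (Section 2.3): 1/40 = 2.5 points

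**The case against.** The strongest objection is reach. As far as the layout of the Section 16.2 schedules shows, the Adverse Events row carries no screening mark and only continuous collection, whereas concomitant medications are marked at screening. Screening is mostly within 14 days of first dose. A condition starting a month or more earlier would ordinarily be medical history, which has its own row. When AE recording begins is a protocol matter that the SAP does not settle. This stands as a limit on how many records are affected. It does not make the rules correct for the records that exist.

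Three stronger readings are tempting, and the document does not support them.

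- *Partial-date events have no classification.* A reader might infer this from the sentence confining imputed AE dates to two figures. But the General row goes on to allow imputation for assigning data to study periods, and the AE row does exactly that and points to Appendix 4. What remains is a clash of wording to be reconciled.
- *Each misflagged event shifts incidence by 100, 33 or 2.5 points.* These are ceilings. Section 8.1 counts a subject once per preferred term and once for any event, so nothing moves if that subject already has another event in the row. Nor do Sections 8.1 to 8.4 say that the summaries are restricted to flagged events.
- *Start dates after stop dates would corrupt durations or onset times.* The General row bars imputed dates from those derivations and from listings, so the visible effect is confined to the two profile plots.

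It is also fair that the error over-counts toxicity in a non-randomized study, so no between-arm comparison is biased.

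**Conclusion.** The point holds as a defect in the stated rules with a probably small effect. Read literally, Section 16.7.2.1 calls an event On-treatment although its whole recorded month precedes the first dose, and Section 16.4.2 flags an event with a missing start although its recorded stop precedes the first dose. In displays 13.0190 and 13.0191 such a corneal event could be drawn as beginning on the first-dose day.

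The number of affected events is not given, and the absence of a screening mark for AE collection suggests few. Any effect on incidence is at most one subject per event. It also requires that the display uses the flag and that the subject has no other event in that row. The conclusion on Section 16.7.2.1 rests on taking the AE row's On-treatment clause at its word. The conclusion on Section 16.4.2 does not depend on that reading.

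**What to change.** Three changes of wording:

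1. **Section 16.7.2.1, missing start day.** Substitute the treatment start date only when the recorded month and year equal those of first dose *and* the AE stop date is missing or on/after first dose. If the recorded month is earlier, or the stop date precedes first dose, use the first of the month and classify the event as pre-treatment. The stop-date condition is needed as well as the same-month condition. Without it, the April event that stopped on 10 April would still be misflagged.
2. **Section 16.4.2, second criterion.** Change it to: *AE start date is missing and the AE stop date is missing or on/after first dose.*
3. **Section 16.7.2.1, General row.** State that imputed AE start dates are also used to set the treatment-emergent flag, so that this row, the AE row and the sentence on study time periods agree.

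The cost is a few lines of SAP text and a minor programming change. No new data are needed, and events whose timing is truly unknown remain treatment-emergent.

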33. Optional follow-up telephone interview to explore visual symptoms and changes in symptoms and related impacts following treatment discontinuation be performed at least 6 months following the End of Study Treatment visit. This interview would only be for those subjects who experienced corneal symptoms during treatment and consent to participate.
34. End of treatment visit should be performed within 30 days (+7 days) after the last dose or prior to the start of new anti-cancer treatment, whichever is earlier. In cases where more than 30 days (+7 days) have elapsed from the date of the subject's last dose due to dosing delays and a subsequent decision to take the subject off treatment, the end of study treatment visit should be scheduled as soon as possible to allow the final assessments to be performed at the earliest date.

35. Participants with corneal signs or symptoms at the end of study treatment visit should be monitored by ophthalmic exam once a month after the last study dose until deemed clinically stable by an eye care professional complete resolution or for 12 months (whichever comes first). Corneal exams to include BCVA and slit lamp examination (with special focus on cornea). Participants who have completed treatment or the 3 month follow up visit (end of study) will be re-consented for additional ophthalmology follow up.

Abbreviations:

ADA = Antibody Drug Antibody; ALP = alkaline phosphatase; BCVA = best corrected visual acuity; BNP = B-type natriuretic peptide; C1D1 = Cycle 1 Day 1, etc.; cfDNA = Circulating free DNA; CK = creatinine kinase; CRP = C-reactive protein; EM = extramedullary; EOI = End of Infusion; FLC = free light chain; PD = Pharmacodynamics; PK = Pharmacokinetics; QID = 4 times a day; SOI = start of infusion; SPEP = serum protein electrophoresis; UPEP = urine protein electrophoresis

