13.0160	All Treated	SAFE_F1	Proportions of Subjects with Infusion-related Reactions (Part 1)	Report for sub-population: Part 1. Pool all subjects together.	SAC [A]
13.0161	All Treated	SAFE_F1	Proportions of Subjects with Infusion-related Reactions (Part 2 MM)	Report for sub-population: Part 2 MM.	SAC [A]
ECG					
13.0200	All Treated	OECG4	Fridericia's QTc Shifts from Baseline to Worst-case Post Baseline (Part 1)	Report for sub-population: Part 1. Pool all subjects together. If machine read QTcF is missing, use the manual read QTcF and add footnote that Machine and Manual calculate values are	SAC [A]

Safety: Figures					
No.	Population	IDSL / Example Shell	Title	Programming Notes	Deliverable [Priority]
				collapsed together.	
13.0201	All Treated	OECG4	Fridericia's QTc Shifts from Baseline to Worst-case Post Baseline (Part 2 MM)	Report for sub-population: Part 2 MM. If machine read QTcF is missing, use the manual read QTcF, and add footnote that Machine and Manual calculate values are collapsed together	SAC [A]
13.0202	All Treated	OECG4	Fridericia's QTc Shifts from Baseline to Worst-case Post Baseline (Part 2 NHL)	Report for sub-population: Part 2 NHL. If machine read QTcF is missing, use the manual read QTcF, and add footnote that Machine and Manual calculate values are collapsed together	SAC
Patient Profile Plot					
13.0190	All Treated	SAFE_F2	Profile Plot for Patients with No Corneal Event or Only Grade 1 Corneal Event (Part 2 MM)	Report for sub-population: Part 2 MM.	SAC [A]
13.0191	All Treated	SAFE_F2	Profile Plot for Patients with Grade 2 or Higher Corneal Events (Part 2 MM)	Report for sub-population: Part 2 MM.	SAC [A]

NOTES:

A. Indicates which displays will be generated for the reporting effort for multiple myeloma

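### The rule for an adverse-event stop date with the day missing caps it at treatment stop even when the recorded month is later, so the two corneal profile plots can draw an event ending before the month the site recorded

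*SAP*

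**What the plan says.** SAP 16.7.2.1 covers dates with month and year but no day, which the eCRF allows "to be recorded for AE start and end dates; that is, the day of the month may be missing". For a stop date of this kind the rule is "Last day of the month will be used, unless this is after the stop date of study treatment", and when it is later the treatment stop date is used. For a missing start day the rule takes the first of the month, or the treatment start date if the first of the month is earlier, and then counts the event as on-treatment.

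The general part of the same section limits where these dates go. "Imputed partial dates will not be used to derive study day, duration (e.g. duration of adverse events), or elapsed time variables". It adds "The imputed AE dates will only to be used in the figures" and names two corneal profile plots. These are Figures 13.0190 (no corneal event, or grade 1 only) and 13.0191 (grade 2 or higher) in 16.12.9, both for the Part 2 myeloma cohort.

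For that cohort, footnote 35 of the schedule in 16.2.3.1 says that subjects with corneal signs or symptoms at the end-of-treatment visit "should be monitored by ophthalmic exam once a month after the last study dose", for up to 12 months. The treatment-emergent flag in 16.4.2 has a lower date limit (treatment start) but no upper one.

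**The concern.** A partial-date rule should fill in the missing part and leave the recorded part alone. This one replaces the recorded month and year whenever month-end falls after treatment stop. If the recorded month is the month of treatment stop, the result still lies within what the site wrote. If it is any later month, the result contradicts the record.

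The plan applies the missing condition elsewhere. In the next part of 16.7.2.1, on follow-up anti-cancer therapy, the date of last dose is used only when the partial date falls in the same month as that dose.

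Affected events are plausible in this cohort. Corneal findings are followed after treatment, and the end-of-treatment visit may itself fall 30 (+7) days after the last dose (footnote 34), so even a resolution recorded at that visit can belong to a later month. For such events the plots would show the toxicity clearing when the drug stopped, although the record places the end later.

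**Working it through.** The plan gives no figure on this point, so there is nothing to reproduce. The rule can be applied as written.

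**Inputs**
- Rule (16.7.2.1): imputed stop = min(last day of recorded month, treatment stop date).
- Use (16.7.2.1 and 16.12.9): Figures 13.0190 and 13.0191 only.
- Assumed for illustration: all calendar dates below, with the date of last dose taken as the treatment stop date.

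**Formula.** The true end lies between the first and last day of the recorded month. When that month is wholly after treatment stop, the error in the plotted end runs from (first day − treatment stop) to (last day − treatment stop).

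**Example 1.** Last dose 10 January 2018, stop recorded as June 2018 without a day.
- Imputed stop = min(30 June 2018, 10 January 2018) = 10 January 2018.
- To 1 June: 21 + 28 + 31 + 30 + 31 + 1 = 142 days.
- To 30 June: 142 + 29 = 171 days.

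**Example 2.** Treatment stop 10 March 2017, with a range of recorded stop months.

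| Recorded stop month | Stop under the rule | Month-end | Plotted end too early by (days) |
|---|---|---|---|
| Feb 2017 | 28 Feb 2017 | 28 Feb 2017 | cap not reached |
| Mar 2017 | 10 Mar 2017 | 31 Mar 2017 | −9 to 21 (within recorded month) |
| Apr 2017 | 10 Mar 2017 | 30 Apr 2017 | 22 to 51 |
| Jun 2017 | 10 Mar 2017 | 30 Jun 2017 | 83 to 112 |
| Sep 2017 | 10 Mar 2017 | 30 Sep 2017 | 175 to 204 |
| Mar 2018 | 10 Mar 2017 | 31 Mar 2018 | 356 to 386 |

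The four later months all collapse to one date. Once the recorded month is after treatment stop, the error can only shorten the event.

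**Onset after treatment stop.** With the same treatment stop, an event starting 5 April 2017 and recorded as ending in June 2017 receives an end of 10 March 2017, which is before its start.

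**What the rule does not reach**
- Study day, duration and elapsed time: imputed dates are barred (16.7.2.1). The corneal onset and duration tables (3.0180 to 3.0183) are therefore unaffected.
- The exposure-response dataset (16.10.1) sets the duration of a resolved corneal event to −99 when its end date is imputed.
- Listings show partial dates as captured (16.7.2.1).
- Events with a full stop date, and events with no stop date at all, which are not imputed.

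**The case against.** The strongest reply is that this is a drawing convention in two descriptive figures, with no reported statistic behind it. That stands, and it limits the weight of the point.

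A reader might infer that every corneal event resolving in follow-up is drawn as ending at treatment stop. The documents do not support this: only events with a recorded month and no day are affected. Their number is not given and may be small, since a resolution found at a monthly examination could carry that visit's full date.

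A reader might also infer that the plan conceals persistence of corneal toxicity. It does not. Section 8.7 summarises visual acuity and corneal signs at the last follow-up examination (Tables 3.0490 to 3.0503). Listing 1.0270 gives the corneal events, Listing 30.0810 gives visual acuity and corneal findings for subjects examined in follow-up, and the OSDI and NEI-VFQ-25 scores after end of treatment are listed.

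Two further limits are fair. The shell for both figures (SAFE_F2) is not shown; if its time axis stopped at end of treatment, a wrong end beyond it would not be visible. The figures also belong to the primary-analysis display list, and the end-of-study list contains no safety figures, so an error near 12 months needs follow-up of that length by the primary-analysis cut.

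On the start rule, the schedules appear to have no screening entry for adverse events, so partial starts in a month wholly before treatment should be few, and counting them as on-treatment is cautious for safety. That limb is secondary. None of this makes the stop rule right for the events it does cover.

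**Conclusion.** The point holds in limited form. As written, the rule gives a wrong end date to any adverse event whose stop day is missing and whose recorded stop month is wholly after treatment stop. The result precedes the recorded month, and precedes onset if the event began after the last dose. The error is 142 to 171 days in the January to June 2018 example. In the second example it runs from 22 to 51 days for the month after treatment stop, up to 356 to 386 days a year later.

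The effect is confined to Figures 13.0190 and 13.0191. The conclusion rests on the literal wording of 16.7.2.1 and on those figures plotting adverse-event end dates beyond treatment stop. The purpose of the imputation implies that they plot these dates, but the shell is not available to confirm the axis. How many events are affected cannot be determined from the documents. The rule should be corrected because it contradicts recorded data and is cheap to change, and not because any reported estimate is at risk.

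**What to change.** In 16.7.2.1, replace the rule for a missing stop day with: use the last day of the recorded month, limited only by the date of death or last contact, never by the treatment stop date, and never earlier than the event's start date.

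As a secondary change, substitute the treatment start date for a missing start day only when the partial start falls in the same month and year as treatment start; otherwise use the first of the recorded month.

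The cost is two sentences in the SAP and a small program change for two figures. Some plotted events will become longer, including those whose recorded stop month is the month of treatment stop, which will now run to month-end. No table, listing or dataset duration changes.
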